The Control Oral Word Association (COWA)⁹ will be used to assess phonemic fluency, which is considered an executive function. Participants will be read a letter ("F", "A", and "S") and asked to generate as many non-proper nouns beginning with that letter as possible within sixty seconds. The outcome measure is the total number of correct words produced for each letter.

Table 1: Study Variables and Their Measurement

Independent variables	Hypothesis	Measurement Instrument	Data*
Demographics		Questionnaire	I
Health status measures:			
▪ Illness severity/comorbidity		Comorbidity Index	I
▪ Use of medications		Medication review	MR, I
▪ Cognitive status		Mini-Mental State Examination (MMSE) Hopkins Verbal Learning Test – Revised (HVLT-R) Digit Symbol Substitution Trails A and B Forward and Backward Digit Span Letter-Number Sequencing Control Oral Word Association (COWA)	I I I I I I
▪ PTSD		Primary Care PTSD Screen	I
▪ Pain		Geriatric Pain Measure (GPM) pain intensity subscale	I
Dependent variables: Outcomes			
Intervention process measures:			
▪ Beliefs and attitudes about sleep	4	Dysfunctional Beliefs and Attitudes about Sleep (DBAS-16) scale	I
▪ Beliefs and attitudes about OSA and PAP	4	Self-efficacy, Knowledge and Decisional Balance Index subscales	I
Subjective sleep measures			
▪ Self-rated sleep quality	1, 3	Pittsburgh Sleep Quality Index (PSQI)	I
▪ Severity of insomnia symptoms	1, 3	Insomnia Severity Index (ISI)	I
▪ Daytime sleepiness		Epworth Sleepiness Scale (ESS)	I
▪ Sleep onset latency, wake after sleep onset		Sleep diary	SR, I
Objective sleep measures:			
▪ Total sleep time, nighttime & daytime sleep percent	1, 3	Wrist actigraphy	M
Quality of life measures:			
▪ Health-related quality of life	2, 3	MOS 12-item Short-form Health Survey (SF-12v2); EuroQol-5D	I
▪ Depressive symptoms	2, 3	Patient Health Questionnaire Depression module (PHQ-9)	I
▪ Anxiety		Patient Health Questionnaire Generalized Anxiety module	I
PAP adherence			
▪ Hours of PAP use per night	1, 3	PAP memory card or modem download	M

*Data source: I=interview, MR=medical records, M=monitoring, SR=self report

- Comorbidity Index¹⁰: The Comorbidity Index is a validated, self-report measure of physical and mental comorbidity. This 36-item self-report questionnaire has a 30-item physical component and a 6-item mental component and was developed for a population of Veterans. Comorbidity index score and individual comorbid conditions will be used as independent variables.

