Sleep diary: Participants will complete a 7-day sleep diary at baseline and follow-up assessments (timed to occur at the same time as wrist actigraphy), which will be used to calculate self-reported sleep onset latency (SOL, time to fall asleep) and wake after sleep onset (WASO, the time spent awake from sleep onset to final awakening) as dependent subjective measures of sleep (see Appendix 2).

- Health-related quality of life

The Medical Outcomes Study 12-item Short-form Health Survey v2 (SF-12v2)¹⁶ will be used as a measure of health-related quality of life. The SF-12v2 Health Survey is a 12-item version of the prior SF-36 (therefore with less participant burden) with evidence for improved format and precision. The SF-12v2 can be scored as a global scale, in 8 domains (physical functioning, physical, bodily pain, general health, vitality, social functioning, emotional and mental health) or as two summary scores (Physical Component and Mental Component Summary Scores). Most population-based descriptive studies of sleep and quality of life have used the longer 36-item version, and very few trials of behavioral interventions for insomnia have included quality of life as an outcome measure at all; these factors make the choice among these scales difficult. In addition, the recently published recommendations for standard research assessment in insomnia trials described above specifically mention the SF-36 as a recommended/essential measure of health-related quality of life.¹ However, after careful consideration of the balance in participant burden and precision, and our own experience with the SF-12v2 in our current work, we have chosen this scale for the current study. We will use the global score, and the Physical Component Summary score and Mental Component Summary score at baseline and follow-up assessments as dependent measures of health-related quality of life.

The EuroQol-5D (EQ-5D)¹⁷ will be used as another measure of health-related quality of life. This 5-item questionnaire was developed by the EuroQol Group in order to provide a simple, generic measure of health for clinical and economic appraisal. The EQ-5D included 5 dimensions: mobility, self-care, usual activities, pain/discomfort and anxiety/depression. Total EQ-5D score at baseline and follow-up assessments will be used as a dependent measure of health-related quality of life.

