For the proposed study, we calculated sample size based on the outcome at post-treatment, and either the reported effect size (d) or d calculated from the reported means and SDs. The table below lists sample size needs for the entire duration of the study (i.e., 6 months). Based on an expected 15% loss by six months, the 5th column in the table below projects the sample size needed for each of 2 groups at randomization to maintain sufficient sample size at 6 months to test the selected outcomes.

Table 5 lists expected effect size, shown as the variable “d” (difference between intervention and control groups at follow-up divided by standard deviation). For many outcomes, we list several expected effect sizes from the literature; references for these effect sizes are listed in the second column. The effect size estimates take into account expected change in controls over time, since we expect controls will change, but not as much as the intervention group. The sample size needed at randomization to detect effect size d is shown (column 4), followed by the number of enrolled participants needed for the 6-month analyses (column 5), taking into account expected dropout by this time point. Based on these calculations, 120 randomized participants (60 per group) will be adequate for analyses at both 3 and 6 months. In addition to these main analyses, we will perform follow-up subgroup analysis to identify two or three variables which identify participants who have the greatest positive response to the intervention. Testing for subgroups with better or worse response results in such a small sample that overfitting is a potential problem; this risk is discussed below.

For example, in Table 5 the third row (WASO by sleep diary) shows that to have the needed sample size (N=19 per group) completing the study (i.e., with follow-up assessment data) to test for an effect (based on an expected 15% participant loss by 6 months), we need to enroll 22 participants per group (column 5) at baseline to have 19 participants per group remaining at 6 months follow-up. For all variables listed, we expect an adequate sample size to test our hypotheses. For all sample size calculations, the dropouts are assumed not to change on average. All testing assumes a two-sided .05 significance level with 80% power.

Table 5: Sample size calculations

Outcome	Reference	Reported (or calculated) effect size d	Enroll per group for d: post-test	Enroll per group for d at 6 months
WASO				

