Sleep diary	Germain ^{Error! Bookmark not defined.}	.67	19	22
Sleep efficiency				
Sleep diary	Espie ^{Error! Bookmark not defined.}	.68	13	15
	Germain ^{Error! Bookmark not defined.}	.64	16	19
Actigraphy	Edinger ^{Error! Bookmark not defined.}	.60	27	32
Sleep onset latency				
Sleep diary	Espie ^{Error! Bookmark not defined.}	.58	20	23
	Germain ^{Error! Bookmark not defined.}	.80	10	12
Sleep quality				
PSQI, similar scales	Edinger ^{Error! Bookmark not defined.}	.58	20	23
	Germain ^{Error! Bookmark not defined.}	1.37	10	12
PAP adherence				
	Cochrane Review ^{Error! Bookmark not defined.}	.59	47	54
	Olsen ^{Error! Bookmark not}	.55	54	62

	defined.			
	Richards ^{Error! Bookmark not defined.}	1.12	14	16
Depression				
Hamilton Depression Scale	Germain ^{Error! Bookmark not defined.}	.67	14	16
Quality of life				
SF-36	Buysse ^{Error! Bookmark not defined.}	.57	50	58

Hypothesis 2: Compared to control participants, participants randomized to the intervention will report fewer depressive symptoms and better health-related quality of life at 3-months follow-up.

This hypothesis tests for differences between the intervention and control groups in depressive symptoms (using the PHQ-9) and health-related quality of life (using the SF-12v2) between baseline assessment and 3-months follow-up. All outcomes will be assessed using intention to treat analyses in an identical manner as described for Hypothesis 2. For sample size calculations, we used data from studies that used the same instrument as planned for the current proposal (if available) or from studies where similar measures were used, if results from the identical measure were not available (see Table 5).

Hypothesis 3: Compared to control participants, participants who receive the intervention will maintain improvements in sleep, PAP adherence, mood and quality of life at 6-months follow-up.

This hypothesis tests for differential change in outcomes between the intervention and control groups from baseline to follow-up assessment at 6 months, to test for maintenance in differences between intervention and control groups in the key sleep, PAP adherence, depressive symptoms and quality of life outcomes at 6 months follow-up. The statistical analyses used will be the same as described for Hypotheses 1 and 2.

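### Hypothesis 2 does not say which quality-of-life score decides: any of three SF-12v2 scores, and on Table 1 also the EQ-5D, could carry that half of the claim at two-sided .05

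*Combined protocol and SAP*

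**What the plan says.** Under Analysis Plan and Hypotheses, Hypothesis 2 predicts that intervention participants "will report fewer depressive symptoms and better health-related quality of life at 3-months follow-up". The analysis text below it tests differences "in depressive symptoms (using the PHQ-9) and health-related quality of life (using the SF-12v2) between baseline assessment and 3-months follow-up". It names the SF-12v2 as an instrument but no score from it, and it does not mention the EQ-5D.

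The baseline measurement section on health-related quality of life is wider. For the SF-12v2 it says "We will use the global score, and the Physical Component Summary score and Mental Component Summary score at baseline and follow-up assessments", all as dependent measures. It then adds: "Total EQ-5D score at baseline and follow-up assessments will be used as a dependent measure of health-related quality of life". Table 1 puts the two instruments in one row, "MOS 12-item Short-form Health Survey (SF-12v2); EuroQol-5D", and assigns that row to Hypotheses 2 and 3.

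On error control, the text before Table 5 says "All testing assumes a two-sided .05 significance level with 80% power". The Hypothesis 1 text attaches Bonferroni to post-hoc comparisons in the time-by-group analysis and Tukey to tests within a time point. The Hypothesis 2 method statement refers to itself: "All outcomes will be assessed using intention to treat analyses in an identical manner as described for Hypothesis 2". Hypothesis 3 asks whether the benefits are maintained at 6 months, using the same analyses.

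**The concern.** The quality-of-life half of Hypothesis 2 is one claim with three or four candidate scores. None is ranked and none is labelled supportive. The protocol does demote measures elsewhere: anxiety is to be explored only, and the circadian actigraphy variables are kept out of the main outcomes. No such label is put on any quality-of-life score.

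The scores can disagree. An insomnia programme could plausibly move the mental summary and leave the physical summary, the global score and the EQ-5D unchanged. As written, the report could then claim better quality of life on whichever score reached .05. Table 5 does not settle the matter, because its quality-of-life row is a single effect size from an SF-36 study with no score named.

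**Working it through.** **Inputs.** From the documents: two-sided .05 per test and 80% power; three SF-12v2 scores, the EQ-5D and PHQ-9; 60 per group randomized and about 51 per group left after 15% loss; d = .57 for quality of life and d = .67 for depression (a Hamilton scale result). Assumed: a common correlation r between the test statistics, from 0 to .9.

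**1. The plan's own figure.** For the Table 5 quality-of-life row, n = 2(1.96 + 0.8416)² / 0.57² = 48.3, so 49 per group. The t-based version gives 49.3, so 50, which matches the stated 50. The 6-month figure of 58 equals 50 × 1.15 = 57.5 rounded up (50/0.85 would give 59). The row therefore describes one test of one score at .05.

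**2. Quality-of-life half, any score sufficient, no true effect.** At r = 0 the chance is 1 − 0.95^k: 14.3% for k = 3 and 18.5% for k = 4. For r > 0, multivariate normal statistics were simulated with 1,000,000 draws and |z| > 1.96:

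| r | three SF-12v2 scores | plus EQ-5D |
|---|---|---|
| 0 | 14.3% | 18.5% |
| .5 | 12.6% | 15.6% |
| .7 | 10.9% | 13.0% |
| .9 | 8.4% | 9.4% |

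Treating the global score as an exact sum of the two component scores, and leaving out the EQ-5D, gives 11.5%, 10.6%, 9.7% and 8.6% at component correlations of 0, .3, .5 and .7. The excess over 5% does not depend on counting the global score as a separate piece of information.

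**3. Depression half.** This is one PHQ-9 total score, so the rate is 5%.

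**4. Both halves required, no true effect anywhere.** PHQ-9 plus at least one of four quality-of-life scores: 0.9% at r = 0, 2.3% at .5, 3.2% at .7 and 4.2% at .9. There is no inflation.

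**5. Both halves required, depression effect real, quality of life null.** With d = .67 and 51 per group, PHQ-9 reaches .05 about 92% of the time. At r = 0 the false quality-of-life half then passes in 0.92 × 14.3% ≈ 13% of trials (three scores) or 0.92 × 18.5% ≈ 17% (four scores). Simulating the same case gives 10.4% and 13.0% at r = .5, 8.0% and 9.7% at .7, and 4.8% and 5.5% at .9. As the PHQ-9 effect grows, these rates approach those in step 2.

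**6. Power for d = .57 at 51 per group** (t-test; the normal approximation is 1 to 2 points higher): 81% at .05, and 63% if alpha were split over four scores at .0125. At 60 per group the .05 figure is 87%.

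**The case against.** The strongest reply is the wording itself. Hypothesis 2 joins its two parts with *and*. If both are required, step 4 shows a rate below 5% when nothing works. That is correct, and it limits the point. It does not remove it: no joint success rule is written down, Table 5 sizes the two outcomes separately, and *and* does not choose among the quality-of-life scores once PHQ-9 has passed.

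A second reply is that the self-reference is evidently a slip for Hypothesis 1, so Bonferroni and Tukey carry over. They probably do, but neither is stated to act across outcomes, so neither governs the choice of score.

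A third is that these are not the primary outcomes. The Hypothesis 1 text does give that place to nighttime sleep and PAP adherence at 3 months, so some priority is stated. This lowers the stakes, but Hypothesis 2 remains a formal claim.

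Three stronger readings are tempting, and the documents do not support them:

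- **Any of five measures suffices, making a false claim about three times as likely as stated.** The PHQ-9 section does call depression another component of quality of life, and the five-measure rate would be about 10 to 23%. But the Hypothesis 2 text treats mood and quality of life as separate outcomes, no any-one rule is given, and the plan states only a per-test level, so there is no stated overall rate to multiply.
- **Month 6 adds another full set of chances, about 30% in total** (correlation .5 between measures and .6 between visits, both assumed). Hypothesis 3 concerns maintenance. Requiring the same measure at both visits gives about 5% under those assumptions.
- **Hypothesis 2 must be tested only after Hypothesis 1 succeeds.** The plan gives no success rule for Hypothesis 1 on which such a gate could rest, and a gate would cost power. It is not needed to repair this point.

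**Conclusion.** The concern holds for the quality-of-life half only. With no deciding score, that half can be claimed falsely at about 8 to 14% on the SF-12v2 alone, or about 9 to 18.5% if the EQ-5D counts as Table 1 implies, against 5% per test. The range rests on assumed correlations and on any one score being enough. If PHQ-9 must also pass, the excess disappears when all effects are null. It returns when the depression effect is real, except at very high correlation, where the rate is close to 5%. The depression half is sound as planned. The disagreement between Table 1 and the Hypothesis 2 text over the EQ-5D needs reconciling whichever rule is chosen.

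**What to change.** In the Hypothesis 2 text, before any arm-level data are seen:

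1. Name one SF-12v2 score as the deciding quality-of-life measure at 3 months and, for maintenance under Hypothesis 3, at 6 months.
2. State that each half is judged on its one named measure (PHQ-9 total; the named SF-12v2 score), and that Hypothesis 2 as a whole is met only if both reach two-sided .05.
3. Report the other two SF-12v2 scores and the EQ-5D as supportive estimates with confidence intervals that cannot by themselves support the claim.
4. Align Table 1 with this, say which score the Table 5 row stands for, and correct the self-reference.

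This is a change of wording only. Each half is then held at 5%, and the whole hypothesis at no more than 5% if either half is null. If the halves are also reported as two separate claims, the chance that at least one is false can reach 1 − 0.95² = 9.75% when the tests are independent, and the text should say that control is per claim. No alpha is split, so quality-of-life power stays about 81% at 51 per group. Requiring both halves has power of about 0.92 × 0.81 = 75% if the tests are independent; the plan's *and* already implies that cost. The main downside is that an effect seen only on an unnamed score cannot be claimed.

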We expect that the group by time analysis of covariance for the sleep variables will show a difference between groups, and post-hoc analyses will show increased nighttime sleep efficiency and improved self-reported sleep (indicated by lower PSQI scores) in the intervention group compared to the control group. Following review of graphical representation of our longitudinal results (on main outcome measures), we will use repeated measures ANCOVA models to test both linear and nonlinear (i.e., quadratic) differential changes over time. Post-hoc tests within each time point (using Tukey type 1 error control) will be conducted. We expect there will be no difference between intervention and control groups at baseline, but differences will be present at follow-up. Other participant characteristics will be considered as possible covariates to reduce bias in our estimate of treatment effects and to increase precision. The major covariates that we expect to consider are age, cognition (estimated by MMSE) and comorbidity (estimated by CIRS-G). Other covariates we will consider include specific diagnoses and medications that may interfere with sleep, and measures of the intervention process (DBAS-16 scores, Self-efficacy, Knowledge and Decisional Balance Index subscales).

Sample size calculations were performed for each of the main outcome variables using reported effect sizes and/or calculated effect sizes from reported sample means and standard deviations reported in the literature in prior studies of CBT-I for insomnia and behavioral PAP adherence interventions in outpatient adults (see Table 5). Prior literature indicates that CBT-I is an extremely potent intervention for insomnia, and the studies typically have large effect sizes and small samples. Some caution is warranted, however, since efficacy studies usually employ tightly controlled ‘ideal’ treatment conditions, which also yield larger effect sizes

than effectiveness studies with more ‘real world’ conditions. Regardless of these issues, even the most conservative estimates of effect size from the literature suggest we will have an adequate sample size to test our sleep outcomes. A recent meta-analysis of trials of PAP adherence interventions published as a Cochrane review was used in estimating sample size for the PAP adherence component of our intervention.^{Error! Bookmark not defined.} this analysis suggests we will have an adequate sample size to test our PAP adherence outcomes.

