Hypothesis 4a: Among intervention participants, improvements in beliefs and attitudes about sleep and OSA will be associated with improved nighttime sleep and better PAP adherence at 3- and 6-months follow-up.

Hypothesis 4b: Intervention participants will identify factors that act as facilitators or barriers to their participation and adherence with the intervention.

We will measure (in both the intervention and control groups) participants' beliefs and attitudes about sleep (using the DBAS-16) and OSA and PAP therapy (using the Self-efficacy, Knowledge and Decisional Balance Index subscales). We will test for differences between groups in these scales between baseline and 3-months follow-up using analysis of covariance (as described above under Hypothesis 1). These scales will also be included as covariates in secondary analyses of main study outcomes to address the effect of "dose" of intervention received on particular participant outcomes (e.g., nighttime sleep and PAP adherence). Within the intervention group, we will also review specific aspects of the process of the intervention (e.g., sleep diary data on bedtime, rise time, in-bed time and daytime napping) to further clarify whether key aspects of the intervention were implemented by participants.

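### Hypothesis 4a is an association within the intervention arm, but none of the analyses listed under Hypothesis 4 tests it as stated

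*Combined protocol and SAP*

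**What the plan says.** In the Analysis Plan, Hypothesis 4a states: "Among intervention participants, improvements in beliefs and attitudes about sleep and OSA will be associated with improved nighttime sleep". The sentence goes on to add PAP adherence as a second outcome. The time points are 3 and 6 months. The population is the intervention arm, the exposure is improvement in beliefs, and the outcomes are sleep and PAP adherence.

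The text beneath lists three quantitative steps:

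1. "We will test for differences between groups in these scales between baseline and 3-months follow-up using analysis of covariance".
2. "These scales will also be included as covariates in secondary analyses of main study outcomes". The stated aim is to gauge how much of the intervention was received.
3. "Within the intervention group, we will also review specific aspects of the process of the intervention". The examples are sleep diary items such as bedtime, rise time and napping.

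Three other places bear on the point:

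- The opening of the Analysis Plan promises models of which covariates predict each outcome. It names no arm, scale or change score.
- The Hypothesis 1 text lists, among covariates to consider for less biased and more precise treatment-effect estimates, "measures of the intervention process (DBAS-16 scores, Self-efficacy, Knowledge and Decisional Balance Index subscales". It does not limit them to baseline values.
- Table 1 assigns the belief scales to Hypothesis 4 as dependent variables, and Table 5 has no row for 4a.

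**The concern.** A reader who carries out the listed steps will not have estimated the quantity that 4a names. A group difference in beliefs shows that the intervention moved beliefs. It does not show that participants whose beliefs improved more slept better or used PAP more. A belief coefficient from a model with both arms answers 4a only if the belief-outcome slope is the same in both, which the plan neither states nor tests.

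A related problem sits in the Hypothesis 1 text. The intervention is meant to change the belief scales, so adjusting a treatment-effect model for their follow-up values would remove part of the effect being estimated.

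**Working it through.** **Matching each step to 4a**

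| Step | Intervention arm only? | Uses belief change? | Sleep or PAP outcome? | 3 and 6 months? |
|---|---|---|---|---|
| Between-group ANCOVA of scales | No | Yes, as outcome | No | 3 months only |
| Scales as covariates | Not stated | Not stated | Yes | Not stated |
| Diary review | Yes | No | Diary process items | Not stated |

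No row meets all four conditions.

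**Sample available.** Sample size estimates: 120 randomized, 60 per group, 15% loss by 6 months. 120 × 0.85 = 102 and 60 × 0.85 = 51 per group, which reproduces the plan's figures.

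**Detectable correlation.** Fisher z, with the plan's two-sided .05 and 80% power: r = tanh[(1.960 + 0.842)/√(n − 3)].

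- n = 51: tanh(2.802/√48) = .384.
- n = 60: tanh(2.802/√57) = .355.
- n = 51 with two adjusters: tanh(2.802/√46) = .391.
- n = 51, Bonferroni over 24 tests: .05/24 gives z = 3.078, so tanh[(3.078 + 0.842)/√48] = .512.

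The 24 is 3 outcomes (PSQI, actigraphy sleep efficiency, share of nights with at least 4 hours of PAP use) × 4 scales (DBAS-16 and three PAP subscales) × 2 time points.

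**Power at n = 51**, one unadjusted test, Φ[atanh(r)·√48 − 1.960]. The r values of .2, .3 and .4 are assumed.

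- r = .2: 29%.
- r = .3: 57%.
- r = .4: 84%.

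The documents give one relevant size. The description of the PAP subscales says that the Decisional Balance Index explained 17% of adherence variance in earlier adjusted analyses. √.17 = .41, for which power is 86%. That figure concerns a score taken one week into PAP, not a change score, so it is only a rough guide.

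**What the listed tests can tell apart.** Simulation with 51 per arm and 5,000 runs. Assumed: group differences of 0.6 SD in both belief and outcome, and the within-arm correlations shown. Entries are the percentage of runs with p < .05.

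| r intervention / r control | Covariate in model with both arms | Correlation within intervention | Between-group test of beliefs |
|---|---|---|---|
| 0 / 0 | 5 | 5 | 85 |
| 0 / .4 | 52 | 5 | 85 |
| .4 / 0 | 52 | 85 | 85 |
| .4 / .4 | 99 | 85 | 85 |

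The between-group test gives the same answer whether 4a is true or false. The both-arm covariate cannot separate row 2 (4a false) from row 3 (4a true).

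**Adjusting for follow-up beliefs.** Adjusted effect = outcome difference − slope × belief difference. With the same assumed 0.6 SD differences and a common slope of .2, .3 or .4, the group effect falls from 0.60 to 0.60 − .2 × 0.60 = 0.48, to 0.42, or to 0.36.

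**The case against.** The strongest reply is that belief-outcome modelling is planned. The covariate step puts the scales into models of sleep and PAP adherence, and such a coefficient is a belief-outcome association. The opening of the Analysis Plan adds predictor models. This stands: a reader might infer that 4a is left wholly untested, and the documents do not support that. What is missing is the arm, the change score and the time point.

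A reader might also take it as settled that the covariate step pools the arms. The reference to main study outcomes makes that likely, but the aim of gauging the intervention received leaves a within-arm reading open. The simulated contrast between arms is likewise an assumption. It shows why the model must be specified, not what will happen.

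The between-group belief test is legitimate. The measures section presents it as a check on the intervention process, and nothing says it will be reported as evidence for 4a.

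Measuring beliefs and outcome at the same visit is no contradiction, since 4a claims association only. Using post-treatment change is a better choice, not a correction of an error.

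Finally, the secondary covariate analyses under Hypothesis 4 are not over-adjusted treatment-effect models. That issue belongs to the Hypothesis 1 text, which lists these scales only as covariates to consider.

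**Conclusion.** The concern holds in this form: no listed analysis tests Hypothesis 4a as stated, and the nearest one is under-specified. This rests on the text, not on a figure.

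A proper test is feasible but limited. With 51 completers it has 80% power for r of about .38, and about 29% power at r = .2. It would be tempting to quote .38 as the detectable size for the whole hypothesis. It applies to one unadjusted correlation, and the requirement rises to about .39 with two adjusters and about .51 under Bonferroni over 24 tests.

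4a is a process hypothesis. A reader might infer that the main results are at risk, but the intention-to-treat comparisons do not depend on it. They would be affected only if follow-up belief scores entered the treatment-effect models, which the Hypothesis 1 text permits but does not require.

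**What to change.** Under Hypothesis 4:

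- Specify a regression within the intervention arm, or the intervention-arm slope from a group-by-belief-change model. The outcomes are PSQI, actigraphy sleep efficiency and the share of nights with at least 4 hours of PAP use, each at 3 and 6 months. The predictor is baseline-to-post-treatment change in DBAS-16 and in each PAP subscale. Adjust for the baseline scale score and, for sleep, the baseline outcome.
- Label the results associational and exploratory. Name one lead scale-outcome pair per domain, or state a multiplicity rule.
- Give r of about .38 only as the detectable size for a single unadjusted correlation at n = 51, with the .39 and .51 figures beside it.
- Keep the between-group belief test as a process check, and say that it is not evidence for 4a.

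Under Hypothesis 1, allow only baseline DBAS-16 and PAP subscale scores as covariates in treatment-effect models.

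The cost is SAP wording and some further secondary regressions: up to 24 scale, outcome and time combinations if no lead pairs are named. Table 4 shows the scales already collected at baseline and post-treatment, so no new data are needed. Power for modest associations stays limited.
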